9.7. Physical Examination

A Physical examination will be performed at Baseline, Month 1, 3, 6, 9 and 12 and One and Two Weeks Post Last Dose Follow Up visits. This will include physical examination of the following body areas and systems: Head, Eyes, Ears, Nose, Mouth, Throat, Neck (including Thyroid); Thorax; Abdomen; Urogenital; Extremities; Neurological; Skin and Mucosae; and Other.

This document is confidential.

A physical exam is optional at unscheduled visits, per the investigator's discretion.

The Physical examination results will be summarized at each visit. All physical examination data will be presented in a listing.

9.8. Other Safety

9.8.1. Columbia Suicide Severity Rating Scale (C-SSRS)

The C-SSRS is a low burden (approximately 5 minutes for completion) instrument to assess both suicidal behavior and ideation. The scale is appropriate for subjects from age 6 through to an elderly population.

The number and percentage of subjects with suicidal behavior and ideation will be summarized at all visits during the treatment, end of study/early termination and follow up visits.

All questionnaire data will be displayed in a listing.

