8.2. Subject Exclusion Criteria

- 1) Subjects with a clinical presentation and/or history consistent with another neurologic condition that may have had accompanying abnormal movements (e.g., Huntington's disease, Parkinson's disease, Wilson's disease, stroke, Restless Legs Syndrome).
- 2) History of schizophrenia, bipolar disorder, or other psychotic disorders.
- 3) Any unstable primary mood disorder (DSM-5 criteria) at time of Baseline.
- 4) Subjects who have unstable medical illness or clinically significant abnormalities on laboratory tests or ECG at Baseline as determined by the Principal Investigator.
- 5) Subjects who have moderate to severe renal insufficiency at Screening.
- 6) Subjects with a major depressive episode in the past 2 years.
- 7) Subjects with a history of attempted suicide.
- 8) A significant risk of committing suicide based on history, routine psychiatric status examination, Investigator's judgment, or who had an answer of "yes" on any question other than 1–3 (currently or within the past 30 days) on the baseline/screening version of the C-SSRS.
- 9) Subjects with a history of seizures (excluding febrile seizures that occurred <2 years prior to Baseline).
- 10) Subjects with a myocardial infarction within 6 months.

- 11) Female subjects who are currently pregnant or lactating or planning to become pregnant during the course of the study.
- 12) Subjects who have a need for medications which would have unfavorable interactions with ecopipam, e.g., dopamine antagonists or agonists [including bupropion], tetrabenazine, monoamine oxidase inhibitors, or St. John's Wort.
- 13) Subjects with current or recent (past 3 months) DSM-5 substance use disorder (with the exception of nicotine).
- 14) Subjects with positive urine drug screen for cocaine, amphetamine, methamphetamine, benzodiazepines, barbiturates, phencyclidine (PCP) or opiates at Baseline, except those receiving stable, prescribed treatment for ADHD. Subjects with urine positive only for benzodiazepines will be exclusionary unless medically prescribed.
- 15) Subjects with a lifetime history of bipolar disorder type I or II, dementia, schizophrenia, or any other psychotic disorder.
- 16) Inability to swallow tablets.
- 17) Subjects with a known hypersensitivity to ecopipam or any of its excipients.
- 18) Any subject who in the opinion of the investigator is not a suitable candidate for the study.

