8.3. Subject Withdrawal Criteria

The Investigator or subject themselves may stop study treatment at any time for safety or personal reasons.

Any subject with a CDRS-R assessment indicative of the onset of a new depressive episode at any visit can be discontinued from study participation at the discretion of the Investigator. Any subject with a new positive response on questions 4 and/or 5 of the C-SSRS will be immediately discontinued and evaluated for risk. Dosing may be restarted at the discretion of the Investigator following consultation with the Sponsor or its designee.

Where possible, a subject who discontinues treatment will undergo the protocol-specified end-of study procedures at the time of discontinuation. Date and reason(s) of premature discontinuation will be described on the CRF. In addition, the date of last dose of study treatment will be recorded on the Study Treatment Dosing CRF.

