4.3. Other Safety Endpoints

- Changes from baseline in Columbia Suicide Severity Rating Scale (C-SSRS) results.
- Changes from baseline in Abnormal Involuntary Movement Scale (AIMS) results.
- Changes from baseline in Barnes Akathisia Rating Scale (BARS) results.
- Changes from baseline in Children's Depression Rating Scale-Revised (CDRS-R) results.
- Changes from baseline in Pediatric Anxiety Rating Scale (PARS) results.

This document is confidential.

5. Analysis Sets

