6.1. General Methods

All analyses and outputs will be produced using SAS® version 9.4 or later. Continuous variables will be summarized using the number of observations (n), mean, standard deviation (SD), median, minimum, and maximum. Categorical variables will be summarized using frequency counts (n), and percentages.

All relevant subject data will be included in listings. All subjects entered the database will be included in subject data listings. All by visit summaries will use the nominal visit. Unscheduled visits will not be summarized but will be included in the listings.

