	14.3.1.8.2	Summary of Adverse Events of Special Interest (AESI) for Ecopipam by System Organ Class and Preferred Term	Safety Set
	14.3.1.9.1	Summary of Most common (>=5%) Adverse Event First Onset by Month	Safety Set
	14.3.1.9.2	Summary of Most common (>=5%) Adverse Events by Month (new incidence or ongoing)	Safety Set
14.3.4.1		Clinical Laboratory Data	

This document is confidential.

Header	Table Number	Name	Analysis Set
	14.3.4.1.1.1	Clinical Laboratory Results Summary: Hematology	Safety Set
	14.3.4.1.1.2	Shift from Baseline Summary: Hematology	Safety Set
	14.3.4.1.2.1	Clinical Laboratory Results Summary: Serum Chemistry	Safety Set
	14.3.4.1.2.2	Shift from Baseline Summary: Chemistry	Safety Set
	14.3.4.1.3.1	Clinical Laboratory Results Summary: Urinalysis	Safety Set
	14.3.4.1.3.2	Shift from Baseline Summary: Urinalysis	Safety Set
	14.3.4.1.4.1	Clinical Laboratory Results Summary: HbA1c	Safety Set
	14.3.4.1.4.2	Shift from Baseline Summary: HbA1c	Safety Set
14.3.4.2		Vital Signs	
	14.3.4.2.1	Vital Signs Summary	Safety Set
14.3.4.3		Electrocardiogram (ECG) Data	
	14.3.4.3.1	12-Lead Electrocardiogram Summary	Safety Set
	14.3.4.3.2	12-Lead Electrocardiogram Overall Interpretation Summary	Safety Set
14.3.4.4		Abnormal Physical Examination Results by Visit	
	14.3.4.4.1	Physical Examination Summary	Safety Set
14.3.4.5		Other Safety Data	
	14.3.4.5.1	Summary of Columbia Suicide Severity Rating Scale (C-SSRS)	Safety Set
	14.3.4.5.2	Summary of Abnormal Involuntary Movement Scale (AIMS) Total Score	Safety Set
	14.3.4.5.3	Summary of Barnes Akathisia Rating Scale (BARS)	Safety Set
	14.3.4.5.4	Summary of Children's Depression Rating Scale – Revised (CDRS-R) Raw Summary Score	Safety Set
	14.3.4.5.5	Summary of Pediatric Anxiety Rating Scale (PARS) Total Score	Safety Set
		Post-Hoc Analysis	
	14.3.4.6a	Shift from Baseline Summary: BMI z-score	Safety Set
	14.3.4.6b	Shift from Baseline Summary: Height z-score	Safety Set
	14.3.4.6c	Shift from Baseline Summary: Weight z-score	Safety Set
	14.3.4.7a	Shift from Baseline Summary: 12-Lead Electrocardiogram QTC	Safety Set
	14.3.4.7b	12-Lead Electrocardiogram Outliers	Safety Set

This document is confidential.

Statistical Analysis Plan for Interventional Studies

Sponsor: Emalex Biosciences, Inc.; Protocol No.: EBS-101-OL-001

Header	Table Number	Name	Analysis Set
	14.3.4.7c	Vital Sign: Heart Rate Outliers	Safety Set
	14.3.4.8	Shift from Baseline Summary: HbA1c	Safety Set

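### SAP 9.8.1 tabulates the C-SSRS visit by visit only and plans no count of subjects with any, or new or worsened, suicidal ideation or behaviour after baseline

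*SAP*

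**What the plan says.** - **Endpoint.** SAP 4.3 lists "Changes from baseline in Columbia Suicide Severity Rating Scale (C-SSRS) results" among the other safety endpoints.
- **Analysis.** SAP 9.8.1 plans this: "The number and percentage of subjects with suicidal behavior and ideation will be summarized at all visits during the treatment", together with "end of study/early termination and follow up visits". Baseline is not named among the summarised visits, whereas SAP 9.8.2 to 9.8.5 name it for the AIMS, BARS, CDRS-R and PARS. The table index (SAP section 14) holds one C-SSRS table, 14.3.4.5.1. The remaining C-SSRS outputs are listings.
- **Unscheduled visits.** SAP 6.1: "Unscheduled visits will not be summarized but will be included in the listings".
- **Entry.** Protocol 8.2, criterion 8, excludes a yes to a C-SSRS question outside 1–3, current or in the past 30 days. A yes on questions 1–3 does not by itself exclude. Criterion 7 excludes "Subjects with a history of attempted suicide".
- **On treatment.** Protocol 8.3: "Any subject with a new positive response on questions 4 and/or 5 of the C-SSRS will be immediately discontinued and evaluated for risk". The next sentence allows dosing to restart at the investigator's discretion after consultation with the sponsor.
- **Adverse events.** Protocol 13.2.1 names suicidality as an adverse event of special interest (AESI). SAP 9.3 has an AESI group for depression together with suicide and self-injury, and counts each patient once per system organ class and once per preferred term.

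**The concern.** The primary objective is long-term safety and tolerability, and suicidality is one of the signals of most interest. The protocol reports that the Phase 3 obesity studies were discontinued because of psychiatric adverse events including suicidal ideation (5.2.2.1). It also reports that suicidal ideation was seen on ecopipam in both the blinded and the open-label paediatric studies (5.3.1).

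For a one-year extension, a reader will ask how many subjects had ideation or behaviour at any time on treatment, and in how many it was new or worse than at entry. A row of visit percentages answers neither question. The same percentages could come from a few subjects positive throughout, some of them already positive at baseline, or from different subjects at each visit. The C-SSRS is the systematic instrument for this question, so leaving its incidence untabulated would weaken the study's main safety statement on this topic.

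**Working it through.** The documents state no C-SSRS rate, sample size or target, so there is no planned figure to reproduce. The check is mainly textual, with one illustration.

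**1. Endpoint against method.** SAP 4.3 promises change from baseline. SAP 9.8.1 gives number and percentage at each visit. No C-SSRS table is a shift table, an any-time count or a new-or-worsened count.

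**2. Entry status.** Questions 1–3 may be positive at baseline, so a later positive on those questions need not be new. With baseline unnamed in the summary, the table as described may not even show the starting percentage.

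**3. Who is in each column.** Under SAP 12.2.5.2, percentages by default use subjects with an observation, so a subject who stops attending leaves later denominators. A positive recorded only at an unscheduled visit enters no column (SAP 6.1).

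**4. The adverse-event route.** SAP 6.2 defines treatment-emergent events as those starting or increasing in intensity on or after the first open-label dose, and the AESI table counts patients once. That is an incidence, but of reported events. Protocol 12.4 finds events by spontaneous report, open question or observation. Protocol 12.1 does require detected signs of abuse, withdrawal or dependence to be recorded as adverse events. There is no matching rule for a positive C-SSRS.

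**5. What visit percentages can and cannot fix.** Let p be the percentage positive at each of k = 12 monthly visits, with complete data. The values of p are assumed.

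- Same subjects every time: ever positive = p.
- Different subjects every time: ever positive = k × p.
- Visits independent: ever positive = 1 − (1 − p)^k.

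| p per visit (assumed) | Minimum, p | Independent, 1 − (1 − p)^12 | Maximum, 12 × p |
|---|---|---|---|
| 1% | 1% | 1 − 0.99^12 = 11.4% | 12% |
| 2% | 2% | 1 − 0.98^12 = 21.5% | 24% |
| 3% | 3% | 1 − 0.97^12 = 30.6% | 36% |

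The newly positive proportion is looser still. It runs from 0%, if every positive was already positive at baseline, up to the same maximum.

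**6. Precedent inside the SAP.** Heart-rate outliers (9.5), ECG outliers (9.6) and YGTSS response (8.1) are each summarised per visit and also overall. HbA1c, total cholesterol (9.4) and QTc (9.6) have shift tables. The C-SSRS has neither.

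**The case against.** The best defence is that suicidality does have a planned incidence. New or worse suicidality reported as an adverse event is treatment-emergent and is counted once per patient in the AESI and preferred-term tables. This stands, so a reader who infers that the plan never counts suicidality as incidence goes too far. The defence does not supply a C-SSRS count, because the step from a positive scale to an adverse event is left to reporting. The nearest rule, in Protocol 12.2.1, makes a test abnormality an adverse event if, for example, it requires stopping study medication. Its examples are laboratory values, vital signs, ECG and physical examination, not rating scales.

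Three other stronger readings are tempting and are not supported:

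- **That all on-treatment positives are confounded with entry status.** Recent positives outside questions 1–3 and any history of attempted suicide are exclusions, so ideation on questions 4–5 and behaviour on treatment would be largely new. The mixing mainly concerns questions 1–3.
- **That discontinuation erases the event.** A positive at a scheduled visit stays in that visit's column. Early-termination and follow-up visits are summarised, SAP 6.4 assigns early-termination scale data to the next scheduled visit, and dosing may restart. What is lost is the accumulation over visits, not the single record.
- **That unscheduled C-SSRS assessments are the ones prompted by concern.** The documents do not say so. They show only that unscheduled results stay out of summaries.

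It is also fair to say that the listings allow a count by hand, and that the AIMS, BARS, CDRS-R and PARS sections likewise describe no change-from-baseline summary. Neither point provides the missing C-SSRS table.

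**Conclusion.** The point holds as a gap in the C-SSRS analysis, not as a claim that the whole plan ignores the incidence of suicidality. SAP 4.3 names change from baseline, and SAP 9.8.1 with its single table cannot show how many subjects had any, or new or worsened, ideation or behaviour on the scale. The one planned incidence depends on adverse-event reporting.

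The size is unknown. As an illustration, 1% positive at each of 12 visits is compatible with 1% to 12% of subjects ever positive. The 11.4% under independence lies near the top of that range, and persistence of ideation within subjects would pull the figure down, so it should not be read as the expected value. The range assumes a constant visit percentage and complete data; with dropout the denominators change and these bounds no longer apply exactly.

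The documents do not state the recall period of the C-SSRS at post-baseline visits, so whether each column is a point or an interval figure is also open. The gap can be closed with data already collected.

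**What to change.** For Safety Set subjects with a baseline and at least one post-baseline C-SSRS, add to Table 14.3.4.5.1 the number and percentage with:

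- (a) any post-baseline ideation;
- (b) any post-baseline behaviour;
- (c) new or worsened ideation, meaning a higher ideation item (1–5) than at baseline, and new behaviour, meaning none at baseline.

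Add a shift table from baseline to worst post-baseline category. Use every post-baseline assessment, including unscheduled ones, and show treatment and follow-up separately. State the look-back period used for baseline, since (c) depends on it, and report how many Safety Set subjects lack a baseline or post-baseline assessment.

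The cost is one extra table with no new data collection. SAP section 10 already records additions made after database lock, so if this is added after lock it must be labelled post hoc.

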9.8.2. Abnormal Involuntary Movement Scale (AIMS)

AIMS records the occurrences of tardive dyskinesia (TD) in subjects receiving neuroleptic medications. The test is used to detect TD and to follow the severity over time. It consists of rating the presence and severity of movement disorders involving the face, mouth, extremities, and trunk as well as three items of global judgment from a scale of 0 (none) to 4 (severe).

The AIMS total score will be calculated by summing the severity of the 10 items that are rated on a scale of 0 to 4. The total score will be summarized at Baseline, Months 1, 2, 3, 4, 5, 6, 7, 8, 9, 10, 11 and 12.

All questionnaire data will be displayed in a listing.

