5. INTRODUCTION

5.1. Background on Tourette's Syndrome

[figure not shown]
Tourette's Syndrome (TS) is a neurological disorder characterized by motor or vocal tics that begin in childhood and persist over time (see box below with the Diagnostic and Statistical Manual for Mental Disorders – 5th Edition [DSM-5] diagnostic criteria). The tics are brief in duration, occur spontaneously, and do not show a regular temporal pattern. Further, the tics are not caused by medications, other medical reasons, or confirmed neurological abnormality. They can be consciously suppressed for some time and are exacerbated by stress. Males are more susceptible than females, with a ratio of about 4.1 to 3. Motor tics can include such things as eye-blinking, facial grimacing, mouth movements, head jerks, shoulder shrugs, and arm/leg jerks. In more severe cases, gyrating, bending, pivoting, and dystonic movements are possible. Vocal tics are fast meaningless sounds or noises, and include such things as sniffing, throat clearing, grunting, barks, and squealing. Complex vocal tics can include shouting out of single words, whole sentences or repeating words (echolalia). In small numbers of subjects, explosive obscenities (coprolalia) are possible. 1.2 Diagnosis of TS is complicated because it often co-exists with other psychiatric illnesses. Common co-morbid conditions include attention deficit/hyperactivity disorder (ADHD), obsessive-compulsive disorder (OCD), anxiety, and depression.² These symptoms often mask TS and make diagnosis difficult. Tic severity can range from mild to severe according to its frequency and intensity. The tics have a variable course, with severe bouts interspersed with complete absence of symptoms. Onset of tics is seen early in childhood (average approximately 7 years) and peaks in the teenage years. Vocal tics appear several years after the onset of motor tics. For most subjects, the period of worst-ever tic severity is between 7 and 15 years old, followed by a steady decline in tic severity. As subjects mature, the vast majority of tics will disappear permanently, with a small percentage of subjects having tics that persist into adulthood and require treatment. Complete remission of tics is reported in approximately 50% of subjects. Severe tics are thought to occur only in about 10% of the cases. $\frac{3}{2}$

DSM-V Diagnostic Criteria For Tourette's Syndrome

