12. ASSESSMENT OF SAFETY

12.1. Safety Parameters

Study Visits may be completed in locations other than clinic and/or via remote administration due to restrictions as a consequence of the COVID-19 pandemic or other qualifying event. Safety will be monitored throughout the study at all visits by repeated adverse event (AE) monitoring, vital signs, the Columbia-Suicide Severity Rating Scale (C-SSRS), the Abnormal Involuntary Movement Scale (AIMS), the Barnes Akathisia Rating Scale (BARS), the Pediatric Anxiety Rating Scale (PARS) and Children's Depression Rating Scale-Revised (CDRS-R). In addition to these assessments, at Baseline, Months 1, 3, 6, 9 and 12 safety will also be monitored by clinical and laboratory evaluations and electrocardiogram (ECG) monitoring. At the Follow Up visit, AE monitoring, the C-SSRS, clinical and laboratory evaluations and vital signs will be assessed. Laboratory evaluations will include hematology, chemistry, urine values and HbA1c. A Follow Up phone call will be conducted 30 days after the last dose of study medication to assess AEs. Additional assessments (all visits except the follow up visit) will include the AIMS, the BARS, the CDRS-R and the PARS. C-SSRS will also be assessed (all visits including the Follow Up visit).

The C-SSRS is a low burden (approximately 5 minutes for completion) instrument to assess both suicidal behavior and ideation. The scale is appropriate for subjects from age 6 through to an elderly population.

The AIMS records the occurrences of tardive dyskinesia (TD) in subjects receiving neuroleptic medications. The test is used to detect TD and to follow the severity over time.

Barnes Akathisia Rating Scale (BARS) scale to assess the severity of drug-induced akathisia. Objective and subjective items in the scale measure the level of subject's restlessness.

Children's Depression Rating Scale-Revised (CDRS-R) is a clinically validated rating scale designed to assess psychiatric signs and symptoms of depressions in children and adolescents.

Pediatric Anxiety Rating Scale (PARS) is a clinician-rated instrument for assessing the severity of anxiety symptoms associated with common anxiety disorders and generalized anxiety in children and adolescents.

Vital Signs:

Vital signs will be collected each clinic visit. They include heart rate, blood pressure, orthostatic blood pressure and heart rate (after being supine for 5 minutes and 3 minutes after standing), height and weight.

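### The AIMS total can mix tics with tardive dyskinesia: the rated regions overlap, tic handling is not stated, and the only AIMS table planned is of the total by visit

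*SAP*

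**What the plan says.** Both documents give the AIMS a specific job. Protocol 12.1: "The AIMS records the occurrences of tardive dyskinesia (TD) in subjects receiving neuroleptic medications". SAP 9.8.2: "The test is used to detect TD and to follow the severity over time".

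SAP 9.8.2 describes the content: "It consists of rating the presence and severity of movement disorders involving the face, mouth, extremities, and trunk", together with three global items. It then reduces the scale to one number: "The AIMS total score will be calculated by summing the severity of the 10 items that are rated on a scale of 0 to 4". That gives a range of 0 to 40, with seven non-global items.

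The planned display is the total: "The total score will be summarized at Baseline, Months 1, 2, 3, 4, 5, 6, 7, 8, 9, 10, 11 and 12". SAP 4.3 lists as an endpoint: "Changes from baseline in Abnormal Involuntary Movement Scale (AIMS) results". The index of tables has a single AIMS table, 14.3.4.5.2, for the total score. Items appear only by subject: "All questionnaire data will be displayed in a listing" (Listing 16.2.8.6).

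Protocol 5.1 describes the disease under treatment: "Motor tics can include such things as eye-blinking, facial grimacing, mouth movements, head jerks, shoulder shrugs, and arm/leg jerks". It adds that severe cases can show gyrating, bending and dystonic movements.

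Baseline is the last value before the first open-label dose (SAP 6.2). Subjects reach it after being tapered off parent-study medication (Protocol 7.1).

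**The concern.** Face, mouth and limbs appear both in the SAP's account of what the AIMS rates and in the protocol's account of where motor tics occur. In severe cases the trunk does too. Neither document tells the rater what to do with a movement that is a tic. A reader of Table 14.3.4.5.2 therefore cannot tell whether the total measures dyskinesia alone or dyskinesia plus tics.

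The design makes this matter. Tics are rated off drug at Baseline and on drug afterwards, and there is no concurrent control. If tics enter the total and the drug reduces them, the total falls for a reason unrelated to dyskinesia, and new dyskinesia in some children can be offset. If tics wax, the total can rise without dyskinesia. Long-term safety is the primary objective, and tardive dyskinesia is a named example within a protocol category of special interest (Protocol 13.2.1), so a falling AIMS total could be read as reassurance that it does not provide.

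**Working it through.** The plan gives no numerical target for the AIMS, so there is no figure to reproduce. The check is a comparison of the texts followed by an illustration of size.

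**Region overlap**

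| AIMS region (SAP 9.8.2) | Motor tics (Protocol 5.1) |
|---|---|
| Face | eye-blinking, grimacing |
| Mouth | mouth movements |
| Extremities | arm and leg jerks |
| Trunk | gyrating and bending, in severe cases |

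**Inputs**
- Motor tic score on ecopipam in the earlier paediatric crossover study, PSY302 (Protocol 5.2.2.1): Baseline 18.4, fall of 3.3 at 30 days, SD of change 4.2. On placebo: Baseline 18.3, fall of 1.6.
- T, the AIMS points that tics supply at Baseline: assumed 0, 1, 2, 4 or 8.
- p, the share of subjects with new dyskinesia: assumed 5% or 10%.
- D, the AIMS points added per new case: assumed 4.
- Tic-related AIMS points are assumed to fall in proportion to the motor tic score.

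**Proportional fall in tics**

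f = 3.3 / 18.4 = 17.9%. On placebo, 1.6 / 18.3 = 8.7%.

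**Mean change in the AIMS total**

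Mean change = -(f × T) + (p × D). For T = 4 and p = 5%: -(0.179 × 4) + (0.05 × 4) = -0.72 + 0.20 = -0.52.

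| T | p = 5% | p = 10% |
|---|---|---|
| 0 | +0.20 | +0.40 |
| 1 | +0.02 | +0.22 |
| 2 | -0.16 | +0.04 |
| 4 | -0.52 | -0.32 |
| 8 | -1.23 | -1.03 |

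**Where the sign changes**

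The mean falls when p is below f × T / D. With D = 4 the limit is 4.5% for T = 1, 9.0% for T = 2, 18% for T = 4 and 36% for T = 8. A fall of only the placebo size with T = 4 gives 0.087 × 4 / 4, or about 9%.

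**One subject**

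Scale the tic change to AIMS points with mean -0.179T and SD T × 4.2 / 18.4 = 0.228T, and assume a normal distribution. For T = 8 and D = 4 the net change has mean 4 - 1.43 = 2.57 and SD 1.83. The chance that this subject's total shows no rise despite new dyskinesia is about 8%. It is about 38% if D = 2, and below 0.1% if T = 4 and D = 4. In these cases offsetting is much less likely within a subject than in the group mean, unless the new dyskinesia is mild and the tic contribution large. This is the reason to look at subjects.

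**The case against.** The strongest reply is that the mechanism is conditional. Offsetting occurs only if raters score tics on the AIMS. The documents neither require nor forbid this, and both describe the scale as one for tardive dyskinesia. The scale's rating conventions are in a cited outside source, and no rater training material is among the documents. If tics were excluded, T = 0 and there is no offset. This stands. A reader might infer that falling tics necessarily lower the total, or that the AIMS here is in effect a second tic scale; the documents do not support either. What they do support is that the handling of tics is unstated.

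Second, detection does not rest on the mean total. SAP 6.1 also gives SD, median, minimum and maximum. Items are listed by subject. Adverse events are collected at every visit and tabulated by preferred term (SAP 9.3). A neurological examination is part of each scheduled physical examination (SAP 9.7). This also stands, so the inference that new dyskinesia would go unseen is too strong. The adverse event route has one weakness: Protocol 13.2.1 names tardive dyskinesia and akathisia, but neither special-interest list in the SAP names those terms. Dyskinesia, dystonia and movement disorder appear within a long Parkinsonism list.

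Third, part of the effect is a general limit of means. Even with T = 0, a 5% incidence moves the mean by only 0.20 on a 0 to 40 scale. That is correct, and it is a further argument for a subject-level display.

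Fourth, a reader might infer from Protocol 5.3.2 that this trial is meant to establish a low risk of tardive dyskinesia. That section reviews existing data and leaves full differentiation to a larger and longer Phase 3 programme. The stated objective here is general long-term safety and tolerability.

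**Conclusion.** The concern holds in conditional form. The AIMS is assigned to detect tardive dyskinesia, it rates regions where motor tics occur, the treatment of tics in the rating is not stated, and the only AIMS table is of the total against an off-drug Baseline. If tics are scored, a fall in them can offset new dyskinesia in that table.

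The size depends on T, p and D, none of which the documents give. With D = 4 and 5% incidence, the mean rises or is about flat for a tic contribution of 0 or 1 point and falls for 2 points or more. At 10% incidence it still rises slightly at 2 points and falls at 4 or 8. The 17.9% is a 30-day change from a different study, and proportional transfer to AIMS points is assumed.

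The consequence is a table open to misreading, not a loss of the safety signal. A fall in the total should not be taken as evidence against tardive dyskinesia, and a rise should not by itself be taken as evidence for it.

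**What to change.** 1. In SAP 9.8.2, alongside Table 14.3.4.5.2, add the number and percentage of subjects with any single regional AIMS item rising by 2 or more points from Baseline at any visit. The 2-point threshold is a screening choice, not a figure from the documents, and should be labelled so.
2. List each flagged subject with the item and visit, the change in YGTSS motor score at the nearest YGTSS visit, and any dyskinesia or movement-disorder adverse event. Match AIMS to YGTSS by assessment date: SAP 6.4 assigns an Early Termination visit by each parameter's own schedule, so same-day ratings can carry different months. State a tie rule for Month 2, which lies between YGTSS visits at Months 1 and 3.
3. Report what raters were told about scoring tics on the AIMS. If they were told nothing, say so.
4. State that a fall in the AIMS total is not by itself evidence against tardive dyskinesia.

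A new rater instruction is not proposed for this trial. SAP section 10 records updates made after database lock, so an instruction could not change the ratings.

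The cost is one extra post-hoc table and listing from data already collected, of the same kind as the shift and outlier tables that section 10 added for QTc, heart rate and HbA1c. Some flagged cases will be waxing tics. For AIMS ratings at Months 2, 4, 5, 7, 8, 10 and 11 the nearest scheduled YGTSS is about a month away, so the comparison there is approximate.

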9.8.3. Barnes Akathisia Rating Scale (BARS)

BARS is used to assess the severity of drug-induced akathisia. Objective Akathisia, Subjective Awareness of Restlessness and Subjective Distress Related to Restlessness in the scale measure the level of subject's restlessness, ranging from zero (normal) to 3 (most severe) and are summed yielding a total score ranging from 0 to 9. The BARS also includes a global clinical assessment of akathisia, ranging from zero (absent) to 5 (severe).

The objective, subjective, total of objective and subjective scores and global scores will be summarized at Baseline and every month during treatment for one year. All questionnaire data will be displayed in a listing.

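### The only planned AIMS summary is a 10-item total that mixes regional ratings with three global judgements, so changes in the two cannot be told apart and can offset each other

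*SAP*

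**What the plan says.** SAP 9.8.2 gives the purpose of the scale: "The test is used to detect TD and to follow the severity over time". It describes the content as "rating the presence and severity of movement disorders involving the face, mouth, extremities, and trunk", "as well as three items of global judgment", all on a scale from 0 to 4. The total is "calculated by summing the severity of the 10 items that are rated on a scale of 0 to 4", summarised at Baseline and at each of Months 1 to 12.

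SAP 4.3 lists as an endpoint "Changes from baseline in Abnormal Involuntary Movement Scale (AIMS) results". The SAP's index of tables (section 14) holds one AIMS table, 14.3.4.5.2: "Summary of Abnormal Involuntary Movement Scale (AIMS) Total Score". Item ratings appear only in Listing 16.2.8.6. No regional subtotal and no separate summary of the global items is planned. Protocol 12.1 describes the scale but gives no scoring rule, and SAP section 10 does not mention AIMS scoring.

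The next section, SAP 9.8.3, handles a similar structure differently. "The BARS also includes a global clinical assessment of akathisia", but the BARS total is the sum of three component items (0 to 9), and the global score is summarised beside it rather than inside it.

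**The concern.** The regional ratings record where movement occurs and how severe it is. A global judgement is an overall impression. Once they are added, a given total no longer shows which of them moved, although the stated purpose of the scale is to detect tardive dyskinesia and follow its severity.

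Long-term safety is the primary objective. Protocol 13.2.1 names tardive dyskinesia among the extrapyramidal events of special interest, and Protocol 5.3.2 presents a lower rate than with D2 antagonists as a possible advantage of ecopipam. AIMS is the scale in this plan aimed at that risk. If its one summary can stay flat, or fall, while a regional movement appears, readers of the table would have to go to the item listing to see it.

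**Working it through.** The SAP gives a score range for BARS (0 to 9), CDRS-R (17 to 113) and PARS (0 to 35), but none for AIMS, so there is no AIMS figure to reproduce.

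**Inputs, all from SAP 9.8.2**
- Items in the total: 10, each rated 0 to 4.
- Global items: 3, described on the same 0 to 4 scale.
- Regional items: 10 − 3 = 7. This count is inferred; the SAP does not state it.

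**Step 1. Make-up of the total.**
- Maximum total: 10 × 4 = 40.
- Regional part: 7 × 4 = 28.
- Global part: 3 × 4 = 12, and 12/40 = 30%.

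**Step 2. One affected region at severity s.** Let k (0 to 3) be the number of global items that repeat s, with the others at 0. Then total = s + k·s = s(1 + k).

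| s | k = 0 | k = 1 | k = 2 | k = 3 |
|---|---|---|---|---|
| 1 | 1 | 2 | 3 | 4 |
| 2 | 2 | 4 | 6 | 8 |
| 3 | 3 | 6 | 9 | 12 |
| 4 | 4 | 8 | 12 | 16 |

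The regional sum is s in every cell, so the multiplier runs from 1 to 4.

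**Step 3. Several affected regions.** With m regions and k global items all rated s, total ÷ regional sum = (m + k)/m. At the upper end, k = 3, with all ratings at 2:

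| Regions (m) | Regional sum | 10-item total | Ratio | Global share |
|---|---|---|---|---|
| 1 | 2 | 8 | 4.0 | 75% |
| 2 | 4 | 10 | 2.5 | 60% |
| 3 | 6 | 12 | 2.0 | 50% |
| 7 | 14 | 20 | 1.43 | 30% |

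The possible inflation is largest for movement confined to one region and shrinks as more regions are involved.

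**Step 4. What a total reveals.** A total of 8 can arise from any regional sum from 0 (global sum 8) to 8 (global sum 0).

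**Step 5. Offsetting.** Suppose a new movement appears in one region, rated 2, while each global item falls by 1. The regional sum changes by +2 and the global sum by 3 × (−1) = −3. The total changes by 2 − 3 = −1, so it improves although regional movement has worsened. The values are illustrative; they show that the direction can reverse, not how often it would.

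**The case against.** The strongest reply is that double counting is not shown. The documents do not say what each global item rates. An item that rates something other than the intensity of movement repeats nothing. The SAP also calls the score a total and never presents it as regional severity, so the text does not contradict itself. All of this stands. It limits the size of the point, but the mixing of two kinds of rating in the only planned summary does not depend on it.

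Several stronger readings are tempting, and the documents do not support them:

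- **A reader might infer that each movement is counted four times.** Four is an upper bound. It needs a single affected region with all three global items matching it.
- **A reader might infer that global items dominate the score.** They are 30% of the possible points. They outweigh the regional items only in focal patterns such as the first row of the Step 3 table.
- **A reader might infer that AESI counts or a tardive dyskinesia rate are distorted.** AESIs are adverse-event categories, summarised by system organ class and preferred term (SAP 9.3). No case definition, threshold or test uses the AIMS total.
- **A reader might infer that tics bias the global items in particular.** The tics listed in Protocol 5.1 involve body areas that AIMS also rates, but nothing shows that they affect global ratings more than regional ones.
- **A reader might infer that the BARS rule obliges the same rule for AIMS.** They are different instruments, and the BARS global item has its own 0 to 5 scale. BARS shows only that the SAP already reports a global item separately elsewhere.

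It can also be said that an inflated score errs on the cautious side for safety. That is true when global and regional ratings move together. Step 5 shows that it fails when they move apart.

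Finally, SAP section 10 shows that this plan already carries additions made after database lock, and redefining a safety score at that stage is unattractive. That is a fair reason to keep the 10-item sum visible and to label the new rows.

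**Conclusion.** The point holds as a limitation of the planned summary. Table 14.3.4.5.2 cannot separate a change in regional movements from a change in overall impression, and the two can offset each other.

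Global items supply up to 12 of 40 points. The total is 1 to 4 times the regional sum for a single affected region, and at most 1.43 times when all seven are equally affected. These figures rest on two assumptions: that the 10 items are seven regional plus three global, and that each global item either repeats the regional rating or is zero.

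The consequence is for interpretation. AIMS is summarised descriptively, so no error rate changes, and the item listing lets the regional sum be recovered. The change is still worth making, because the scale addresses a named risk in a study whose primary objective is long-term safety.

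**What to change.** In SAP 9.8.2 and Table 14.3.4.5.2:

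- State which items are regional and which are global, and give the score ranges.
- Summarise the sum of the seven regional items (0 to 28) by visit, with change from baseline, as the main AIMS severity score.
- Summarise the three global items separately, by visit.
- Keep the 10-item sum (0 to 40) as a supplementary row, so that the total as now defined is still reported.
- Record the change in SAP section 10 as made after database lock.

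The cost is SAP wording, a little programming and a few extra table rows. The item ratings are already collected and listed, so no new data are needed. The downside is one more post-lock addition; showing both sums and labelling the change lets a reader judge whether the choice of score matters.
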